12.2 SENSITIVITY ANALYSES OF THE PRIMARY ENDPOINT

For US (FDA) Submission

As sensitivity analyses, the primary analysis of the U.S. (FDA) primary endpoint will be repeated using the ITT2, PPS, and FAS.

For Ex-US Submission

As sensitivity analyses, the primary analysis of the primary endpoint for Ex-U.S. will be repeated using the FAS2, PPS, and ITT.

In addition, the impact of missing data on the analysis of the U.S. primary efficacy endpoint will be examined using the following additional sensitivity analyses as in the ITT population summarized in Table 4. These sensitivity analyses are further detailed in Sections 12.2.1 to 12.2.3.

Table 4. U.S. Primary Endpoint Analysis Results

Hb Value Censoring due to Rescue	Analysis ITT Population	Treatment Difference and 95% CI (pooled roxadustat vs pooled placebo)	Std. Err.	Degree of Freedom*	t-statistics	p-value
No censoring	ANCOVA with Multiple Imputations	.xx (.xx, .xx)	.xxx	xxx	.xxx	.xxxx
	MMRM	.xx (.xx, .xx)	.xxx	xxx	.xxx	.xxxx
	PMM-Last Mean Carried Forward	.xx (.xx, .xx)	.xxx	xxx	.xxx	.xxxx
	PMM-Baseline Carried Forward (Roxa. Only)	.xx (.xx, .xx)	.xxx	xxx	.xxx	.xxxx
	PMM-Baseline Carried Forward (Both Groups)	.xx (.xx, .xx)	.xxx	xxx	.xxx	.xxxx
	PMM-Jump to Control	.xx (.xx, .xx)	.xxx	xxx	.xxx	.xxxx
Set Hb to missing for 6 weeks due to Rescue Medications	ANCOVA with Multiple Imputations	.xx (.xx, .xx)	.xxx	xxx	.xxx	.xxxx
	MMRM	.xx (.xx, .xx)	.xxx	xxx	.xxx	.xxxx

$$df = (m - 1) \left(1 + \frac{m \bar{U}}{(m + 1)B} \right)^2$$

where

*Maximum of Degree of freedom from each individual ANCOVA. The actual Degree of Freedom in PMM was calculated using B is between-imputation variance and U the standard error associated with estimates Rubin (1987).

12.2.1 Change in Hb - MMRM Model

As sensitivity analysis, a mixed model of repeated measures (MMRM) approach will be used. The model will contain terms for treatment arm, baseline Hb and eGFR measurements, visit, treatment*visit, and the other randomization stratification except baseline Hb (≤ 8 vs > 8) and eGFR as fixed effects. The primary efficacy analysis will be based on the estimated difference in the overall mean effect between the two treatment groups throughout the Evaluation Period based on the MMRM model.

The MMRM model will be used to compare the pooled roxadustat vs. pooled placebo. H_0 will be tested at the two-sided $\alpha = 0.05$ level of significance and will be rejected if the $p < 0.05$ from the test.

Due to the large amount of visits (up to week 52) to include in the model, the unstructured covariance pattern model will be applied first. If the algorithm for unstructured covariance pattern does not converge, then the heterogeneous Toeplitz structure will be used instead. If this second model also does not converge, then the (homogeneous) Toeplitz structure will be tried, and finally compound symmetry will be used as the covariance structure to achieve convergence. If none of them converge, first order autoregressive (AR (1)) as a covariance structure will be used to achieve convergence.

12.2.2 Change in Hb - Pattern Mixture Model (PMM)

PMMs provide a general and flexible framework for sensitivity analyses that allows formulating assumptions regarding missing data in a transparent and clinically interpretable manner. This is expected to address the possibility of the data being missing not at random (MNAR).

The following aspects of missing data may affect the estimates.

- Timing and extent of missing data
- Assumed underlying mechanism for missing data

12.2.2.1 Timing and Extent of Missing Data

To assess the potential effect of missing data on the estimate of treatment effect, subjects will be classified as full data or missing data cases. Patterns of missing data will be based on non-missing hemoglobin values in the evaluation period.

- Full data cases are defined as subjects without non-missing hemoglobin for all scheduled weeks of the evaluation period.
- Missing data cases are defined as subjects with a missing hemoglobin value (s) on at least one scheduled assessment in of the evaluation period. The missing data cases are further grouped into intermittent missing and monotone missing cases.

- Intermittent missing hemoglobin cases are defined as subjects with a missing hemoglobin value for at least one scheduled assessment in the evaluation period but not on consecutive scheduled assessments up to the end of evaluation period.
- Monotone missing hemoglobin cases are defined as subjects who have missing Hb values in consecutive scheduled Hb assessments with missing hemoglobin up to the end of evaluation period. A subject who is a monotone missing case could have intermittent missing hemoglobin prior to the ending week.

Subjects will be grouped as follows:

- Full data cases
- Intermittent missing data cases
- Monotone missing data cases

Should the incidence of monotone missing data cases and intermittent missing data cases be relatively small (e.g., <xx%), then those cases will be combined so that the groups are full data cases and missing data cases. The summary of missing pattern in evaluation period will be presented in a table.

12.2.2.2 Assumptions on Missing Data Mechanism

In addition to the extent/amount of missing data, the mechanism under which missing data occur may affect the estimate of the parameter of interest.

The potential impact of missing data on the estimates of treatment effects will be assessed using statistical models with different underlying assumptions on the missing data mechanism (i.e., missing not at random(MNAR)) (Little and Rubin).

12.2.2.3 PMM - Last Mean Carried Forward

A pattern-mixture model using a last mean carried forward multiple imputation method (Carpenter et al, 2013) will be used as another sensitivity analysis to explore the robustness of the ANCOVA results for the primary efficacy variables. Using this method, missing data after ending week will be imputed based on the last non-missing mean from its own treatment group.

The steps to implement this sensitivity analysis are as follows. Parameter below refers to the parameter of the multi-normal distribution for baseline and post baseline Hb measurements.

1. Create posterior distribution of parameter: Separately for each treatment arm, take all patients observed data and assuming Missing At Random (MAR) to fit a multivariate normal

distribution with unstructured mean (i.e., a separate mean for each of the baseline plus post-baseline scheduled weeks and unstructured variance covariance matrix using a Bayesian approach with an improper prior for the mean and an uninformative Jeffreys' prior for the variance-covariance matrix (Schafer, 1997, p. 155).

2. Draw parameters: Separately for each treatment arm, draw variance-covariance matrix from the posterior distribution for the parameters. The mean Vector would be set to the marginal mean for their randomized treatment arm at their last non-missing measurement.
3. Build joint distribution of missing data and observed data: For each subject with missing data, using the draws for the parameter to build the joint distribution of their observed and missing data.
4. Construct conditional distribution of missing data given observed data: For each patient with missing data, use their joint distribution in previous step to construct their conditional distribution of missing data given observed data. Sample the missing data from this conditional distribution, to create a 'completed' data set.

Repeat the above steps for 200 times and resulting in 200 imputed data sets. Then fit ANCOVA model for each imputation data set, and combine the resulting parameter estimates and standard errors using Rubin's rules (Rubin, 1987) for final inference.

12.2.2.4 PMM – Baseline Carried Forward (Roxadustat Only and Both Groups)

The analysis is the same as PMM – Last Mean Carried Forward except imputing the missing data. The imputation data will be generated similarly as last mean carried forward method described above but instead of using post-baseline observed data, only baseline data will be used. The similar analyses will be conduct in two scenarios.

- The baseline carried forward imputation will be performed for the roxadustat treatment group only, while for active control group, the imputation data will be generated using the last mean carried forward described above.
- The baseline carried forward imputation will be performed for the both treatment groups.

Similarly, the Rubin's method will be then used to combine the estimates and the differences between the least square mean differences between the two treatment groups from each of the ANCOVA analysis. This sensitivity analysis will be performed for U.S. primary endpoints only.

12.2.2.5 PMM - Jump to Control

A pattern-mixture model using a last mean carried forward jump to control multiple imputation method (Carpenter et al, 2013) will also be used as another sensitivity analysis similar to the PMM-Last Mean Carried Forward except for step 3, where the joint distribution of the patient's

observed and missing data are considered to be multivariate normal with mean and covariance matrix from the control (placebo) treatment arm.

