9 STATISTICAL CONSIDERATIONS

9.1 Sample Size Determination

A total of up to 1200 planned subjects will be randomized in a 2:1 ratio to receive either roxadustat (approximately 800 subjects) or placebo (approximately 400 subjects) in a double-blind manner.

The study is sufficiently powered for both regionally-based primary efficacy endpoints. A minimum of 450 subjects are planned to be randomized to receive roxadustat or placebo (2:1 with approximately 300 roxadustat vs 150 placebo) in a double-blind manner in order to support the primary endpoint(s) of the study.

For US (FDA) Submission Primary Efficacy Endpoint

A sample size of 450 will have > 99% power to detect a 1 g/dL difference in mean Hb values between the two treatment groups, assuming that the common standard deviation is 1.2 g/dL, using an analysis of variance (ANOVA) test with a 0.05 two-sided significance level.

For the comparisons of individual treatment arms versus pooled placebo, a sample size of 35 roxadustat and 150 placebo will have 90% power to detect a 0.75 g/dL difference in mean Hb values between the two treatment groups, assuming that the common standard deviation is 1.2 g/dL, using an ANOVA test with a 0.05 two-sided significance level.

For Ex-US Submission Primary Efficacy Endpoint

Based on a two-sided test at the $\alpha = 0.05$ level of significance, the study will have > 95% power to demonstrate a statistically significant difference between roxadustat and placebo, assuming that the proportion of subjects with a Hb response in the roxadustat group is at least 65% and the cumulative proportion of subjects with a Hb response in the placebo group is at most 25%.

During the course of this Phase 3 study, which is being conducted in parallel with other Phase 3 studies, up to 1200 subjects may be enrolled in this study to support the overall safety evaluation of roxadustat across pooled multiple studies in the Phase 3 program, including adjudicated composite safety endpoints of interest. The study will stop enrollment at the Sponsor's discretion if: 1) the minimum of 450 subjects has been achieved to support the primary endpoint in this individual study, and 2) sufficient safety events of interest have been accumulated across the nondialysis Phase 3 program to support a pooled analysis of these events across multiple studies in the same population.

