5 GENERAL STATISTICAL CONSIDERATIONS

5.1 SAMPLE SIZE DETERMINATION

A total of at least 450 and up to 1200 planned subjects will be randomized in a 2:1 ratio to receive either roxadustat (at least 300, but at most 800 subjects) or placebo (at least 150, but at most 400 subjects) in a double-blind manner.

The study is sufficiently powered for both regionally-based primary efficacy endpoints. A minimum of 450 subjects are planned to be randomized to receive roxadustat or placebo (2:1 with approximately a minimum of 300 roxadustat vs 150 placebo) in a double-blind manner in order to support the primary endpoint(s) of the study.

For US (FDA) Submission Primary Efficacy Endpoint

A sample size of 450 will have > 99% power to detect a 0.75 g/dL difference in mean Hb values between the two treatment groups, assuming that the common standard deviation is 1.2 g/dL, using an analysis of variance (ANOVA) test with a 0.05 two-sided significance level.

For the comparisons of individual treatment arms for each of the 3 dose frequencies of roxadustat for Hb maintenance versus pooled placebo, a sample size of 35 roxadustat and 150 placebo will have 90% power to detect a 0.75 g/dL difference in mean Hb values between the

two treatment groups, assuming that the common standard deviation is 1.2 g/dL, using an ANOVA test with a 0.05 two-sided significance level.

For Ex-US Submission Primary Efficacy Endpoint

Based on a two-sided test at the $\alpha = 0.05$ level of significance, 450 subjects will have > 95% power to demonstrate a statistically significant difference between roxadustat and placebo, assuming that the proportion of subjects with a Hb response in the roxadustat group is at least 65% and the proportion of subjects with a Hb response in the placebo group is at most 25%.

During the course of this Phase 3 study, which is being conducted in parallel with other Phase 3 studies, up to 1200 subjects may be enrolled in this study to support the overall safety evaluation of roxadustat across pooled multiple studies in the Phase 3 program, including adjudicated composite safety endpoints of interest. The study will stop enrollment at the Sponsor's discretion if:

- 1) The minimum of 450 subjects has been achieved to support the primary endpoint in this individual study, and

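### The SAP's Jump to Control analysis applies the placebo mean to every visit, so roxadustat dropouts keep part of their Hb gain and the result is milder than a jump

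*SAP*

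**What the plan says.** SAP 12.2.2.3 sets out a four-step imputation called Last Mean Carried Forward:

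1. Fit a multivariate normal distribution to baseline and post-baseline Hb, separately by arm.
2. Draw the covariance matrix, and fix the mean vector at the randomized arm's mean at the patient's last non-missing visit.
3. Build the joint distribution of observed and missing Hb.
4. Draw the missing Hb conditional on what was observed.

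SAP 12.2.2.5 introduces its variant as "A pattern-mixture model using a last mean carried forward jump to control multiple imputation method". It is described as similar to the parent method except at step 3, where the patient's "observed and missing data are considered to be multivariate normal with mean and covariance matrix from the control (placebo) treatment arm". Step 4 is not changed, and nothing says what becomes of step 2's mean vector.

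Table 4 in SAP 12.2 gives the analysis its own row. No other row takes its imputation distribution from the placebo arm.

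**The concern.** A jump implies a change at a point in time: own-arm mean up to the last observation, placebo mean afterwards. As written, the placebo mean holds throughout, so there is nothing to jump from. Because step 4 conditions on observed Hb, a roxadustat patient who has responded looks like a placebo patient with unusually high Hb. Any positive serial correlation projects that excess into the missing visits.

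This matters because the primary analysis (SAP 12.1, steps 1 and 2) imputes within arm, so roxadustat dropouts are given the roxadustat course. SAP 13.1.2 itself suspects differential dropout. After early termination, Protocol 7.1.2.6 follows patients for vital status, adjudicable events and key medications, not routine Hb. One CBC is scheduled at End of Study, 4 weeks after early termination (Protocol 7.1.3.1), but SAP Table 17.1-1 gives it its own follow-up visit outside the Weeks 28 to 52 grid. The pattern-mixture rows are therefore the main check on data missing not at random. A reader of this row will take its estimate and interval as the result when benefit is lost at dropout.

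**Working it through.** **The plan's own figure.** SAP 5.1 states "A sample size of 450 will have > 99% power to detect a 0.75 g/dL difference in mean Hb values", with "2:1 with approximately a minimum of 300 roxadustat vs 150 placebo", "assuming that the common standard deviation is 1.2 g/dL" and a two-sided 0.05 test. Standard error = 1.2 × √(1/300 + 1/150) = 0.12. Power = Φ(0.75/0.12 − 1.96) = Φ(4.29) = 99.999%, so the statement reproduces. Protocol 9.1 uses 1 g/dL, which gives Φ(8.33 − 1.96), also above 99.99%. The statement "a sample size of 35 roxadustat and 150 placebo will have 90% power to detect a 0.75 g/dL difference" gives a standard error of 0.225 and Φ(3.33 − 1.96) = 91.5%, close to the stated 90%.

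**What each rule imputes.** Let S be the covariance matrix, with o for observed and m for missing visits.

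- As written: E[missing] = μP(m) + S(mo) S(oo)⁻¹ (y − μP(o))
- True jump: E[missing] = μP(m) + S(mo) S(oo)⁻¹ (y − μR(o))

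For a patient on the roxadustat mean, y − μR(o) averages zero, so a jump leaves no excess over placebo. As written, the excess is S(mo) S(oo)⁻¹ d, where d is the roxadustat-minus-placebo mean at the observed visits.

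**Inputs.** The visit grid is from Protocol 4.5.1: Weeks 0, 1, 2, every 2 weeks from 4 to 24, then every 4 weeks to 52 (21 points, seven of them in Weeks 28 to 52). Assumptions: placebo Hb flat, effect reached linearly by Week 8, equal SD at all visits, correlation as listed below. The share kept then does not depend on the SD or the size of the effect.

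**Correlation decaying at r per 4 weeks.** Only the last observation matters. The share kept at week t after a last Hb at week L is r^((t − L)/4). For r = 0.7 and L = 24, averaging exponents 1 to 7 gives 0.7 × (1 − 0.7⁷)/0.3/7 = 0.306. L = 20 multiplies this by 0.7 (0.214). L = 8 multiplies it by 0.7⁴ (0.073).

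**Constant correlation ρ (compound symmetry).** Share = ρ Σd / (1 + (n − 1)ρ), with d as a fraction of the full effect. For L = 8, n = 6 and Σd = 0 + 0.125 + 0.25 + 0.5 + 0.75 + 1 = 2.625; ρ = 0.3 gives 0.3 × 2.625/2.5 = 0.315. For L = 24, n = 14 and Σd = 10.625; ρ = 0.7 gives 0.7 × 10.625/10.1 = 0.736.

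Share of the effect kept in the imputed Weeks 28 to 52 mean:

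| Correlation | Last Hb Week 8 | Week 20 | Week 24 |
|---|---|---|---|
| 0.5 per 4 weeks | 1% | 7% | 14% |
| 0.7 per 4 weeks | 7% | 21% | 31% |
| 0.8 per 4 weeks | 18% | 36% | 45% |
| 0.9 per 4 weeks | 44% | 60% | 67% |
| 0.95 per 4 weeks | 67% | 78% | 82% |
| Constant 0.3 | 32% | 60% | 65% |
| Constant 0.5 | 38% | 66% | 71% |
| Constant 0.7 | 41% | 69% | 74% |
| True jump, any correlation | 0% | 0% | 0% |

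Mixtures of a persistent and a decaying component gave 24% to 73%. A simulation of 200,000 patients agreed. With last Hb at Week 20 and an effect of 0.75 g/dL, the excess as written was 0.499 (constant 0.5) and 0.160 (0.7 per 4 weeks). The jump was within 0.003 of zero at every setting simulated.

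**Trial level.** If a proportion p of roxadustat patients has no Weeks 28 to 52 Hb and a share f is kept, the difference is 0.75 × [1 − p(1 − f)]. With p = 0.3 (an assumption):

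- f = 0: 0.75 × 0.70 = 0.525 g/dL
- f = 0.3: 0.75 × 0.79 = 0.59
- f = 0.5: 0.75 × 0.85 = 0.64
- f = 0.7: 0.75 × 0.91 = 0.68

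**Effect on the test.** Holding the standard error at 0.12 as an approximation, a true jump has power 99.9%, 99.2%, 96.3% and 87.8% at 20%, 30%, 40% and 50% imputed. Keeping half the effect gives 99.7% or more at each.

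**The case against.** **The size is not in the documents.** This stands. No Hb correlation is given, and if it decays at 0.7 or faster per 4 weeks, about 70% or more of the gain is removed. A reader might infer that dropouts keep most of their benefit. That holds only for slow decay or a strong persistent component with later dropout, and nothing in the plan settles which applies. Only the direction is fixed.

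**A harsher check is already planned.** This also stands. SAP 12.2.2.4 carries baseline forward for roxadustat only, while the control arm uses last mean carried forward. With flat placebo Hb this removes the whole gain; if uncensored rescue raises placebo Hb, it is stricter than a jump. So it would be wrong to infer that loss of benefit goes untested. That analysis asks a different question, though: it returns patients to their own baseline, not to the placebo course.

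**The text is ambiguous, not settled.** This stands in part. The heading, the leftover last-mean label, step 2's own-arm mean and the new step 3 do not fit together, and the cited methods paper may guide the programmer. One cannot say the program will certainly copy placebo means throughout. But that is what step 3 says, and two programmers could reasonably produce different numbers.

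**No conclusion changes.** Largely right. The row carries no alpha, and the type I error of the primary test is untouched.

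**Conclusion.** The rule as written does not deliver the analysis it names. With any positive serial correlation it is more favourable to roxadustat than a jump. For a last Hb at Weeks 8 to 24 the share kept ranges from about 1% to 82% across the correlations tried. At 0.75 g/dL with 30% of roxadustat patients imputed, the row would read roughly 0.07 to 0.16 g/dL too high (0.59 to 0.68 against 0.525) if 30% to 70% is kept. These figures assume flat placebo Hb, an effect complete by Week 8, and imputed patients with no Hb in the evaluation window.

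A reader might go further and infer that the primary result or the trial's conclusion is in doubt. The documents do not support that: the pooled comparison has ample power even under a true jump, and the primary analysis does not use this rule. What is affected is the estimate and interval of the only reference-based row in Table 4. It should be corrected before the analysis is run.

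**What to change.** In step 3 of SAP 12.2.2.5, use the subject's own-arm means for visits up to the last observed Hb and the placebo means for later visits. State the covariance rule that joins the two parts. Delete or explain the last-mean-carried-forward wording, and say whether step 2's mean vector still applies. If the present rule is wanted, relabel it as copying control and add the true jump as a further row in Table 4.

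The cost is a few lines of SAP text, a small program change and a somewhat less favourable sensitivity estimate. No data collection or sample size is affected.

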12.2.3 Hb Censoring After Rescue Therapy

Because the rescue use may potentially confound the effect of roxadustat, analysis will also be performed where Hb values will be censored for 6 weeks (or 8 weeks if during an evaluation period) after rescue therapy use to examine its potential impact on the robustness of the efficacy findings.

All sensitivity analyses for Change in Hb described in the above section will be applied to these scenarios using the ITT Population.

12.2.4 Hb Responder: Logistic Regression

The primary analysis for EX-US endpoint will also be repeated using logistic regression instead of Cochran–Mantel–Haenszel (CMH) test and including in this model the randomization stratification factors excluding baseline Hb and eGFR. Baseline Hb and baseline eGFR will be included as continuous covariates instead of as class factors. The odds ratio (pooled roxadustat versus pooled placebo) and its 95% confidence interval will be provided.

The SAS procedure will be similar to the following:

```
proc logistic;  
  class treatment region cv_history;  
  model response = treatment region cv_history baseline_Hb baseline_eGFR;  
run;
```

This model will also be repeated using logistic regression and adjusting by sex and age, in addition to the factors mentioned above.

The analyses in this section will use the FAS population.

